7.6 Immunosuppressive Therapy-specific risks

Alemtuzumab

Alemtuzumab is known to have a significant risk of cytokine release syndrome. This syndrome can usually be minimized by premedication with steroids but can include fever, chills, malaise, hypotension, tachycardia, and pulmonary edema. Lymphopenia may be associated with increased risk of infection.

Sirolimus

Phase III studies of sirolimus in cyclosporine based regimens have revealed mild dose related thrombocytopenia and increases of serum triglycerides and cholesterol. This latter finding is probably its most consistent effect and was seen in 40-50% of patients. Hypertriglyceridemia predominates. HMG-CoA reductase inhibitors and fibric acid have been used and well tolerated to counteract the hyperlipidemia associated with sirolimus. Additionally, the unexpected finding of nephrotoxicity has been encountered but is likely attributable to sirolimus' potentiation of CNI nephrotoxicity and thus is likely to be inapplicable in this trial. Other common events reported in trials include leukopenia, hypertension, anemia, nausea, vomiting, elevated liver enzymes, rash and acne [37,38] Other risks from the package insert for sirolimus include possible development of lymphoma and other malignancies, particularly of the skin, increased susceptibility to infection including opportunistic infections, fatal infections, and sepsis, and lymphocele, a known surgical complication of renal transplantation, occurring significantly more often in a dose-related fashion in sirolimus-treated patients.

Belatacept in Kidney Transplant Study

Specific risks associated with belatacept may include those typically associated with transplant related immunosuppression including infection and malignancy.

Over 1000 transplant patients have received belatacept in clinical trials. Patients in these trials received belatacept or cyclosporine (a marketed drug for comparison), in addition to basiliximab, mycophenolate mofetil (MMF also known as CellCept), which is an immunosuppressant, and steroids to prevent transplant rejection. In general, patients treated with belatacept had the same overall rate of side effects, including infections and cancers, as patients who received cyclosporine. In the first 36 months of follow-up in the three clinical trials done in kidney transplant patients, the frequency of side-effects was similar comparing belatacept and cyclosporine. The most commonly reported side-effects (in $\geq 20\%$ of subjects) among belatacept subjects were urinary tract infection, diarrhea, constipation, nausea, swelling, decrease in transplanted kidney function, fever, cough, high blood pressure, and low white blood cells count. Some side effects were serious and required hospitalization. Some were fatal. Some side effects were serious and required hospitalization. Some were fatal.

Post-transplant Lymphoproliferative Disorder

Post-transplant lymphoproliferative disorder (PTLD), a tumor of white blood cells that can occur after kidney transplantation, developed more frequently in patients who received belatacept (14 cases out of 949; 1.5% of subjects) than those who received cyclosporine (3 cases out of 476; 0.6%). In addition, more than half of the PTLD cases in belatacept patients involved the brain (9 cases out of 14; 65% of belatacept patients), which is a higher proportion than expected. A total of 11 of 17 subjects with PTLD died; 8 out of 14 in the belatacept group and 3 out of 3 in the cyclosporine group.

PTLD is known to occur after transplant in approximately 1% of adults and is almost always associated with the Epstein-Barr virus (EBV). NULOJIX® (belatacept) is contraindicated in transplant recipients who are Epstein-Barr virus (EBV) sero negative

or with unknown EBV serostatus due to the risk of post-transplant lymphoproliferative disorder (PTLD), predominantly involving the central nervous system (CNS). As the total burden of immunosuppression is a risk factor for PTLT, higher than the recommended doses or more frequent dosing of Nulojix and higher than recommended doses of concomitant immunosuppressive agents are not recommended. Physicians should consider PTLT in patients reporting new or worsening neurological, cognitive, or behavioral signs or symptoms.

The risk of PTLT was higher in EBV sero negative patients compared to EBV seropositive patients. EBV seropositive patients are defined as having evidence of acquired immunity shown by the presence of IgG antibodies to viral capsid antigen (VCA) and EBV nuclear antigen (EBNA). Epstein-Barr virus serology will be ascertained before starting administration of Nulojix, and only patients who are EBV seropositive will receive Nulojix. Transplant recipients who are EBV sero negative, or with unknown serostatus, should not receive Nulojix.

Other known risk factors for PTLT include cytomegalovirus (CMV) infection and T-cell-depleting therapy. T-cell-depleting therapies to treat acute rejection should be used cautiously. CMV prophylaxis is recommended for at least 3 months after transplantation. Patients who are EBV seropositive and CMV seronegative may be at increased risk for PTLT compared to patients who are EBV seropositive and CMV seropositive. Since CMV seronegative patients are at increased risk for CMV disease (a known risk factor for PTLT), the clinical significance of CMV serology for PTLT remains to be determined; however, these findings should be considered when prescribing Nulojix.

The physician will perform tests to see if the patient has antibodies to EBV. If the patient does not have antibodies to the virus, they will not be allowed to enroll in the study. If they do have antibodies to the virus, the physician will counsel them about their risk of developing PTLT. Additional monitoring and the use of anti-viral medications may be prescribed by their physician to help reduce their risk.

Post-transplant lymphoproliferative disease (PTLT) is known to be associated with the degree of immunosuppression. It occurs in approximately 0.7% of adults and up to 4.5% of children following transplantation [39-42]. This condition can give rise to lymphoma in over 50% of those patients in which it occurs. The relative risk of this condition compared to conventional therapy in humans is not known but should be reduced substantially by exclusion of EBV positive to negative mismatches.

PTLT Safety Surveillance

Special surveillance for PTLT will be considered for all subjects in this study. The PTLT safety surveillance should be implemented as soon as IRB/IEC approval and subject consent are obtained.

Subjects with Suspected PTLT

CNS imaging and/or neurologic consultation should be considered for any subject with a new or worsening neurologic finding. For subjects who undergo biopsy for suspicion of

PTLD, we recommend evaluating the biopsy specimen for CD3, CD20, CD79, and EBER. Management of belatacept and other immunosuppressants in subjects with suspected PTLD should be discussed with the BMS Medical Monitor. BMS should be informed of all confirmed cases of PTLD.

Progressive Multifocal Leukoencephalopathy (PML)

Progressive multifocal leukoencephalopathy (PML) is an often rapidly progressive and fatal opportunistic infection of the CNS that is caused by the JC virus, a human polyoma virus. In clinical trials with Nulojix, two cases of PML were reported in patients receiving Nulojix at higher cumulative doses and more frequently than the recommended regimen, along with mycophenolate mofetil (MMF) and corticosteroids; one case occurred in a kidney transplant recipient and the second case occurred in a liver transplant recipient. As PML has been associated with high levels of overall immunosuppression, the recommended doses and frequency of Nulojix and concomitant immunosuppressives, including MMF, should not be exceeded.

Physicians should consider PML in the differential diagnosis in patients with new or worsening neurological, cognitive, or behavioral signs or symptoms. PML is usually diagnosed by brain imaging, cerebrospinal fluid (CSF) testing for JC viral DNA by polymerase chain reaction (PCR), and/or brain biopsy. Consultation with a specialist (e.g., neurologist and/or infectious disease) should be considered for any suspected or confirmed cases of PML.

If PML is diagnosed, consideration should be given to reduction or withdrawal of immunosuppression taking into account the risk to the allograft.

7.7 Therapy Failure

Patients may have an increased risk of graft loss due to rejection should the primary therapy fail. It is not clear if the rate of rejection onset will be significantly faster for patients in this protocol. However, the Sponsor-investigator has extensive experience in managing immunosuppressive reduction trials including those with complete immunosuppressive withdrawal. The Sponsor-investigator and the principal investigator are in close and frequent contact related to the management of this trial. The monitoring of patients in this trial greatly exceeds that in standard practice specifically to minimize the likelihood of a late rapid rejection.

7.8 Phlebotomy

Peripheral blood draws (venipuncture); during this study, blood drawn for research will not exceed 450ml per six-week period. The patient may experience some discomfort at the site of the needle entry, and there is a risk of bruising at the site. There is a remote risk of fainting or local infection.

7.9 Renal Biopsy

Renal biopsy is a standard procedure that carries a low risk for the patient of bleeding. The risk is minimized by guidance with real time ultrasound and decreases with time from the transplant procedure. Biopsies performed within one week of transplant carry a 1-2% risk of significant bleeding (defined as requiring some intervention, either transfusion or surgery). This decreases to less than 0.5% after the 4th week as the kidney scars into place. Transplanted kidneys are easier to biopsy than native kidneys due to their location in the iliac fossa as opposed to in the flank. Biopsy will not be performed on patients with a platelet count <80 unless clinically indicated. A biopsy shall be considered clinically indicated when obtained to evaluate any abnormality and required by the attending physician to guide clinical care.

During a biopsy, a patient will feel mild burning for several seconds during instillation of a local anesthetic agent. Thereafter, the patient will feel a pushing sensation, but usually little pain, as the needle enters the kidney. There may be some mild residual pain. In the event that significant bleeding is suspected, either through clinical observation or a significant decrease in hemoglobin, an ultrasound will be performed. Transfusion will be administered as necessary or the patient will be taken to the operating room for direct control of the bleeding.

8. STUDY OBSERVATIONS

8.1 Flow Charts/Time and Events Schedule

Month 1

| Tests / Evaluations | On Enrollment | | Day 7 Post-transplant (study day 8) | Day 14 (+/- 2 days) post-transplant | Day 21 (+/- 2 days) post-transplant | Day 28 (+/- 3 days) post-transplant |
|----------------------------------------------------------------------|----------------|--|-------------------------------------|-------------------------------------|-------------------------------------|-------------------------------------|
| Informed Consent | X | | | | | |
| Medical History | X | | | | | |
| Demographics | X | | | | | |
| Physical Examination | X | | X | X | X | X |
| Vital Signs | X | | X | X | X | X |
| Confirm Inclusion/ Exclusion criteria | X | | | | | |
| CBC with Differential | X | | X | X | X | X |
| Blood Chemistry/lipids | X | | X | X | X | X |
| Urinalysis | X | | X | X | X | X |
| Serum Pregnancy Test | X | | | | | |
| Sirolimus trough (study) | | | X | X | | |
| Donor-specific Antibody | X | | | | | X |
| Panel Reactive Antibody | X | | | | | X |
| Donor-specific and third party mixed lymphocyte responsiveness/ ICCS | X | | | | | |
| Lymphocyte Subsets-Ki67 | X ^a | | | | | X ^a |
| Peripheral blood transcription | X ^a | | | | | X ^a |
| Informed Consent | X | | | | | |
| HIV Ab | X | | | | | |
| HBsAg and HCV Ab | X | | | | | |
| CMV and EBV PCR | X | | | | | X |
| BK viremia/viruria PCR | X | | | | | X |
| Adverse Events | X | | X | X | X | X |
| QoL | X | | | | | |
| Immunogenicity | X ^a | | | | | |

^a These are specific study related assays for reporting purposes.

Months 2-6

| Tests/Evaluations | Every 2 Weeks | Monthly | Every 3 Months | At 6 Months | With Clinical Biopsies |
|-----------------------------------------------------------------------------------------------------|---------------|---------|----------------|----------------|------------------------|
| Physical Examination | | X | | | X |
| Vital Signs | | X | | | X |
| CBC with Differential | X | X | | | X |
| Blood Chemistry/lipids | X | X | | | X |
| Urinalysis | X | X | | | X |
| Sirolimus trough | x | | | | X |
| Lymphocyte Subsets Ki67 | | | | X ^a | X |
| Peripheral transcription | | | | X ^a | X |
| Donor-specific and third party mixed lymphocyte responsiveness/ other studies of hyporesponsiveness | | | | X | X |
| PRA | | | | X | X |
| Renal Biopsy | | | | X | X |
| Intra graft mRNA analysis | | | | X | X |
| | | | | X | |
| CMV and EBV PCR | | X | | | |
| BK viremia/viruria PCR | | X | | | X |
| Adverse Events | X | X | | | X |
| QoL | | | | X | |
| Neurologic Exam | | | X | | |
| Immunogenicity | | | | X ^a | |

^a These are specific study related assays for reporting purposes.

Long-Term Follow-Up Cohort 1

| Tests / Evaluations | Every 6months | Yearly |
|----------------------------------------------------------------------|----------------------|----------------|
| Telephone Reporting | X | |
| Serum Chemistry/ lipids /CBC | X | |
| Sirolimus trough | | X |
| Lymphocyte subsets | X | |
| Peripheral transcription | | X |
| CMV and EBV PCR | X | |
| BK viremia/viruria PCR | X | |
| PRA | | X |
| Anti-Donor Antibody | | X |
| Donor-specific and third party mixed lymphocyte responsiveness/ ICCS | | X |
| Renal Biopsy | | X ^b |
| Intragraft mRNA Analysis | | X ^b |
| Adverse Events | X | X |
| QoL | X | |
| Neurologic Exam | X | |
| PK | | |
| Immunogenicity | X | |

=

^b To be performed prior to weaning patient to monotherapy (generally at 12 months) and again after stable on monotherapy as clinically indicated.

Long-Term Follow-Up Cohort 2

| Tests / Evaluations | Monthly after Year 1 | Every 3 months from 6 - 24Months | Every 6 months | Yearly |
|----------------------------------------------------------------------|-----------------------------|-----------------------------------------|-----------------------|----------------|
| Telephone Reporting | | | X | |
| Serum Chemistry/ lipids /CBC | X ^c | | X | |
| Sirolimus trough ^d | X | | | X |
| Lymphocyte subsets Ki67 | | | X | |
| Peripheral transcription | | | | X |
| CMV and EBV PCR | | X | X | |
| BK viremia/viruria PCR | | X | X | |
| PRA | | | | X |
| Anti-Donor Antibody | | | | X |
| Donor-specific and third party mixed lymphocyte responsiveness/ ICCS | | | | X |
| Renal Biopsy | | | | X ^b |
| Intra-graft mRNA Analysis | | | | X ^b |
| Adverse Events | X ^e | | | |
| QoL | | | X | |
| Neurologic Exam | | | X | |
| Immunogenicity | | | X | |

^cStudy participants may have these labs drawn more or less frequently as deemed clinical necessary by the investigator.

^dStudy participants who are not weaning sirolimus and are on a stable, low dose can have trough levels monitored as frequently as a monthly basis or as clinically indicated.

^eIf study participant is on a stable dose of sirolimus, not weaning, and receiving commercial belatacept as an outpatient, then adverse events may be assessed every three months.

Year 1 Medication Flowchart

| | Day of Transplant 1 st Dosing Day 1 | Day 2 | Day 4 | Day 8 | Day 14 | Mo 1 | | | | Mo 3 | | | | Mo 6 | | | | Mo 12 | | |
|------------------------------|-------------------------------------------------------------------------------------------------------------------------------------------------------------------------------------------------------------------------------------------------------------------------------------------------------------------------------------------------------------------------------------------------------------------------------------------------------------|-------|-------|-------|--------|------|------|------|-------|-------|-------|-------|-------|-------|-------|-------|-------|-------|-------|-------|
| | | | | | | Wk 4 | Wk 6 | Wk 8 | Wk 10 | Wk 12 | Wk 16 | Wk 20 | Wk 24 | Wk 28 | Wk 32 | Wk 36 | Wk 40 | Wk 44 | Wk 48 | Wk 52 |
| | | | | | Wk 2 | | | | | | | | | | | | | | | |
| belatacept 10 mg/kg | X | | X | X | X | X | X | X | X | X | X | X | X | | | | | | | |
| belatacept 5 mg/kg | | | | | | | | | | | | | | X | X | X | X | X | X | X |
| sirolimus | Sirolimus will be started on post-op day 1 at a dose of 2 mg per day orally. Doses will be adjusted to maintain 24-hour trough levels of 8-10 ng/ml until the drug is weaned as described below. | | | | | | | | | | | | | | | | | | | |
| methylprednisolone 500 mg | X | | | | | | | | | | | | | | | | | | | |
| alemtuzumab 30 mg | X | | | | | | | | | | | | | | | | | | | |
| Prophylaxis | Post-operative viral (oral valganciclovir of duration in keeping the standard of care based on pre-operative donor and recipient CMV status), fungal (oral nystatin or clotrimazole), and bacterial prophylaxis (perioperative surgical prophylaxis transitioning to oral Pneumocystis prophylaxis) dosed for 6 months post transplantation. All prophylaxis agents will be withdrawn at 6 months unless there are specific clinical indications otherwise. | | | | | | | | | | | | | | | | | | | |
| Immunosuppression Withdrawal | During year 2 (weeks 53-104), weaning of immunosuppression will begin for all patients meeting pre-defined criteria. Patients will be first weaned off sirolimus over at least a 2 – 6 month period. After sirolimus, is weaned, patients will remain on belatacept monotherapy indefinitely. | | | | | | | | | | | | | | | | | | | |

9 Details of Research Procedures

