indicates to us that complete immunosuppressive weaning offers an unacceptable risk and we have accordingly altered our protocol to eliminate this as an explicit goal of the trial. It is important to point out that our approach in this situation is substantially different from that taken by the investigators of a recently reported tolerance trial.^{2,109-111} In this trial performed at the Massachusetts General Hospital (MGH), several patients have been weaned from all immunosuppression. However, ABMR led to graft loss in 2 of 10 patients, and DSA formed in several other patients that have been followed expectantly. Endothelial injury has been observed in many patients. From a statistical standpoint, it is not clear if the results from our regimen differ from those of this trial, as we have not pressed forward aggressively to continue pursuing a drug-free state in the face of an asymptomatic DSA. We have viewed the appearance of DSA as an unacceptable risk for late graft loss that should be avoided, and opted not to consider immunosuppression elimination without some evidence that monotherapy belatacept has some risk. We reason that the ultimate goal is graft function without side effects, and that risking graft loss in pursuit of an immunosuppressive-free state without evident benefit over a state maintained with a once monthly CoB-based regimen imposes risk without compensatory benefit. Particularly in the absence of a clear metric identifying patients at risk for ABMR and graft loss, we view complete drug withdrawal to be unsupportable at this time.

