2 STUDY OBJECTIVES

2.1 Primary Objective

This study will determine whether T-cell depletion followed by belatacept and daily maintenance therapy with sirolimus will permit recipients of renal allografts to avoid rejection and eventually be weaned to belatacept monotherapy maintenance immunosuppression. The primary endpoint will be the number of patients successfully withdrawn from sirolimus for 1 year after their last dose of sirolimus. “Successfully withdrawn” will be defined as a patient off sirolimus without clinical or biopsy evidence of rejection.

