4.2 Analyses

Demographics and Baseline Characteristics

Demographic and baseline characteristics of patients will be summarized descriptively by treatment group, by means and standard deviations (SDs) for continuous variables and frequency distribution for categorical variables. Summaries will be performed based on the data set.

Efficacy Analyses

No formal statistical hypothesis testing will be performed for the primary endpoint. All efficacy analyses will generally be descriptive in nature. The primary efficacy analysis will be to assess the proportion of patients successfully withdrawn from sirolimus for one year. The point estimate of this proportion and the exact two-sided 95% confidence interval (CI) will be provided for each treatment group. A patient will be considered to be successfully withdrawn from immunosuppression for one year if the patient has been administered only belatacept for a period of 365 days, following successful completion of sirolimus, and has not experienced biopsy-proven acute rejection, formation of DSA, or graft loss for this same period of 365 days. Secondary efficacy outcome measures involving incidences and proportions will be descriptively summarized with point estimates and exact, two-sided 95% CIs by treatment group. Other secondary efficacy outcome measures will be descriptively summarized by means and SDs for continuous outcomes and frequency distributions for categorical outcomes.

Safety Analyses

All AEs and SAEs will be summarized by treatment group. Laboratory values will also be descriptively summarized.

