6.2 Maintenance Immunosuppressive Reduction

Beginning any time after year 1 (week 53), participants who are deemed eligible for sirolimus withdrawal as determined by clinical and flow cytometric parameters

(described below) may be withdrawn from sirolimus. Withdrawal will proceed at a maximum rate of 66% of the original dose for 4 weeks, 33% of the original dose for another 4 weeks, then discontinued. However, each reduction in dose will be predicated on stable flow cytometric profile.

Criteria for Sirolimus Withdrawal. Participants will be deemed eligible for withdrawal of sirolimus if they meet all of the following criteria:

1. No episodes of steroid resistant acute rejection since transplant, and no episodes of steroid sensitive rejection for 12 months.
2. Stable renal function, as defined by both of the following:
 - a. GFR, using calculated CrCl (Cockcroft-Gault) of > 40ml/min.
 - b. Creatinine, which in the 12 weeks preceding withdrawal has not increased more than 20% with respect to the lowest creatinine observed during the same period.
 - c. Absence of histologic evidence of acute or chronic rejection on pre-withdrawal renal biopsy according to the Banff criteria for acute, chronic and humoral rejection.
3. Absence of DSA reactivity, as measured by de novo anti-donor-HLA antibodies.
4. ALC at least 80% of the baseline ALC prior to alemtuzumab.
5. Ki67 expression on CD3+ T cells that is within 1 standard deviation of the normal expression in untreated controls. Ki67 is typically seen in <3% of lymphocytes in health controls and a value >5% exceeds the value accepted for purposes of this trial.

For determining eligibility, a renal biopsy will be obtained and creatinine clearance will be estimated. Requisite blood samples will be obtained within two weeks before starting sirolimus withdrawal. Results of laboratory assessments of immune status will be made available to, and reviewed by, the investigator. These data will be reviewed with the knowledge of previous results of immunosuppression withdrawal obtained in the current trial up to the time of review.

Maintenance Immunosuppressive Therapy

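### Section 4.2 makes donor-specific antibody formation a primary-endpoint failure, but no antibody sample is tied to either end of the 365-day window

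*Combined protocol and SAP*

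**What the plan says.** Section 4.2 (Efficacy Analyses) calls a patient successfully withdrawn if, over 365 days on belatacept alone after sirolimus, the patient "has not experienced biopsy-proven acute rejection, formation of DSA, or graft loss for this same period of 365 days". Section 2.1 defines the same term as "a patient off sirolimus without clinical or biopsy evidence of rejection", with no antibody component.

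Antibody testing around weaning is described in these places:

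- **Before the taper.** Section 6.2 requires "Absence of DSA reactivity, as measured by de novo anti-donor-HLA antibodies" for eligibility and adds: "Requisite blood samples will be obtained within two weeks before starting sirolimus withdrawal".
- **After the taper.** The long-term schedules in section 8.1 give anti-donor antibody a single yearly mark (Cohort 1: "Anti-Donor Antibody | | X"; Cohort 2 also yearly only). No footnote links the mark to the last sirolimus dose.
- **At biopsies.** Section 9.2 places protocol biopsies three months and one year after weaning. The accompanying blood is for phenotyping and lymphocyte harvest; no serum or DSA assay is named.
- **For cause.** The work-up in section 6.6 starts when rejection is suspected.

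**The concern.** A component of the primary endpoint should be measured over the period in which it counts. Rejection largely meets that standard, because section 9.2 ties biopsies to weaning; flow cytometry is also tied to it, monthly until one year after sirolimus ends. DSA is not. The test before weaning is timed to the start of the taper, whereas the 365-day window opens at its end. The next scheduled test falls wherever the yearly draw happens to fall.

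The for-cause work-up does not close the gap, because DSA can be silent: section 1.3.5 itself refers to decisions made "in the face of an asymptomatic DSA". The same section shows why the component matters: "We have viewed the appearance of DSA as an unacceptable risk for late graft loss that should be avoided". Section 3.3 also lists alloantibody formation as an evaluation criterion. At stake is whether the headline count of successful withdrawals means what 4.2 says it means.

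**Working it through.** **1. The plan's own figures.** Section 3.4: 20 × 0.20 = 4 lost to earlier rejection and 4 more ineligible or refusing, so 20 − 4 − 4 = 12 attempts; 12 × 0.50 = 6 successes. Both figures reproduce. The exact 95% CI for 6/12 is 21.1% to 78.9%.

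**2. Start of the window.** The pre-weaning sample precedes the taper by up to two weeks. The taper takes 8 weeks at the fastest (6.2), at least three months (3.1), or 2 to 6 months (Synopsis and medication flowchart). These passages differ and need reconciling; all were run. On any of them the last negative result is about 2 to 6 months old when the window opens.

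**3. End of the window.** Assumption: yearly draws fall on transplant anniversaries (months 24, 36). With the last dose at month m, the window runs from m to m + 12. For 12 < m < 24 the only draw inside it is at month 24, so the untested tail is (m + 12 − 24)/12.

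| Taper from month 12 | Last dose | Window closes | Untested tail | Close to next draw |
|---|---|---|---|---|
| 2 months | 14 | 26 | 2/12 = 17% (about 61 days) | 36 − 26 = 10 months |
| 3 months | 15 | 27 | 3/12 = 25% (about 91 days) | 36 − 27 = 9 months |
| 6 months | 18 | 30 | 6/12 = 50% (about 182 days) | 36 − 30 = 6 months |

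In weeks, for a week-53 start and tapers of 8, 13 and 26 weeks, the tails are 8.8, 13.8 and 26.8 weeks (17%, 26%, 51%). Across 15 combinations of start (weeks 53 to 104) and taper length, exactly one yearly draw falls in the window each time, with 15% to 99% of the window after it. If the yearly draw is instead made one year after the last dose, the tail is 0.

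**4. Two errors with opposite signs.** Silent DSA in the tail is unseen at day 365. If it is found at month 36, its onset cannot be placed inside or outside the window. Conversely, DSA first seen at month 24 after a negative sample at month 12 may have formed during the taper. The taper occupies 2/12, 3/12 or 6/12 of that interval (17%, 25%, 50%), the same lengths of time as the tails.

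**5. Effect on the estimate.** One patient is 1/12 = 8.3 points (1/20 = 5.0 on the 20 enrolled under 3.1; 1/40 = 2.5 on the Synopsis total). From a true 6/12:

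| Reported | Proportion | Exact 95% CI |
|---|---|---|
| 5/12 | 41.7% | 15.2% to 72.3% |
| 6/12 | 50.0% | 21.1% to 78.9% |
| 7/12 | 58.3% | 27.7% to 84.8% |

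**6. How many patients.** The available text gives no DSA rate (part of the prior-cohort results is withheld). For illustration only, assume a one-year risk q of silent DSA with uniform onset. The expected number arising in the tail is 12 × q × tail. For q = 5%, 10%, 20%, 30% this is 0.1, 0.2, 0.4, 0.6 with a 2/12 tail and 0.3, 0.6, 1.2, 1.8 with a 6/12 tail. Risk during the taper is a separate unknown, so no net figure follows.

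**The case against.** - **Section 2.1 may govern.** If so, DSA is not part of the endpoint and the sampling point falls away. That is a fair condition. But 4.2 specifies the primary analysis and includes DSA, so the conflict has to be resolved in any case.
- **The yearly draw may accompany the one-year biopsy.** Renal biopsy sits in the same column with a weaning-linked footnote. The gap would then be zero at the end of the window, though not at its start. Against this, section 9.3 refers to a year 2 annual visit and counts quality-of-life visits from transplant. Both readings are open, which is itself the defect.
- **Other coverage exists.** Appendix B stains biopsies for C4d, which gives a partial check for antibody-mediated injury. It would not detect circulating DSA without C4d deposition.
- **The analysis is descriptive.** Section 4.2 says: "No formal statistical hypothesis testing will be performed for the primary endpoint". A one-patient shift lies well inside the exact interval, so no test result changes. This stands and limits the weight of the point.

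A reader might infer that late silent DSA is scored as success and that the bias therefore runs upward. The documents do not support that. Section 4.2 turns on formation, not detection by day 365, and states no rule for DSA found later. Follow-up of at least five years means that persistent DSA may surface at a later yearly draw, although undated. DSA formed during the taper can lower the count. Nor does the plan time DSA at the start of the window: the 6.2 sample marks the start of the taper.

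**Conclusion.** The point holds in this form: a component of the 4.2 endpoint has no sample anchored to either end of its window, and the plan has no rule for DSA whose onset cannot be dated. The success count can be wrong in either direction by 8.3 points per patient on 12 attempts. The net direction and the number of patients affected cannot be established.

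The tails of 17%, 25% and 50% rest on the assumed transplant-anniversary anchor and a taper starting at month 12; under other readings the tail runs from 0 to nearly the whole window. The absence of an anchor does not depend on those assumptions.

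Re-timing the samples is a cheap improvement. The conflict between 2.1 and 4.2 over whether DSA counts is wrong as written. The gain is a correctly ascertained headline count, not a changed test.

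**What to change.** 1. In the Cohort 2 schedule (8.1), tie an anti-donor antibody sample to the existing one-year post-sirolimus biopsy visit and take another at the last sirolimus dose. Keep the yearly draws.
2. In 4.2, state that the endpoint uses the one-year biopsy and DSA results within a stated visit window; how DSA first found outside that window is classified; how a missing result is counted; and which rejection date applies. Section 6.6 uses biopsy confirmation, whereas Appendix A uses the start of additional immunosuppression.
3. Reconcile 2.1 with 4.2 on DSA.
4. Reconcile footnote b (printed under the Cohort 1 table, its marker reused in Cohort 2), which makes the later biopsy depend on clinical indication, with 9.2, which schedules post-weaning biopsies. Section 7.9 ties clinical indication to an abnormality, while 9.2 applies the term to protocol biopsies. This review does not say which schedule is right.

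**Cost.** Wording, plus one or two serum tubes and assays for each of about 12 weaned patients, at times when blood is already drawn (the biopsy visit and monthly flow cytometry). At the 10 ml used for baseline serum in 9.1, each tube is 10/450 = 2.2% of the six-week research limit. No biopsy is added. The reported success proportion may be slightly less favourable.
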